4.1.3. Women of Child Bearing Potential

For the purposes of this study, all female participants will be considered as WOCBP unless they have undergone surgical sterilization (with documented hysterectomy, bilateral salpingectomy and bilateral oophorectomy) or are postmenopausal and have a documented serum follicle stimulating hormone level > 35 mIU/mL (with or without hormone replacement therapy) and no menses within the previous 12 months.

WOCBP are permitted in the study but must consent to avoid becoming pregnant by using approved contraception methods throughout the study and for up to 4 weeks after completion, as described below.

Study-acceptable methods of birth control are double-barrier methods, which include a combination of any 2 of the following: systemic contraceptives, diaphragm, condom, any intrauterine device, partner's vasectomy, or sponge with spermicide. Spermicide can be used in combination with any of the other methods listed.

WOCBP must have a negative pregnancy test at all clinic visits.

Daiichi Sankyo must be notified of any study subject who becomes pregnant while participating in this clinical study, as described in Section 9.6.

4.2. Removal of Subjects From Therapy

Data from all randomized subjects are important to achieve study objectives and subjects should be encouraged to adhere to protocol instructions and visit schedules. However, in accordance with the Declaration of Helsinki and other applicable regulations, a subject has the right to withdraw from the study at any time, and for any reason, without prejudice to his or her future medical care by the study physician or at the study site. The Investigator is also free to terminate a subject's involvement in the study at any time if the subject's clinical condition warrants such action. The Sponsor or regulatory authorities also may request termination of the study at any time due to safety issues or concerns related to study conduct.

NOTE: In this study, the C-SSRS will be administered at all clinic visits. Based on the C-SSRS and investigator judgment, if a subject is identified as being at risk for suicide, appropriate safety measures should be implemented (see Section 3.1.5.2).

The MINI and C-SSRS are to be administered at any time during the study (including unscheduled visits) based on investigator's discretion (see Section 3.1.5.2).

4.2.1. Reasons for Withdrawal/Early Discontinuation

Any subject who discontinues from the study treatment for any reason will have their reason for study treatment discontinuation recorded on the eCRF using the following criteria.

For subjects withdrawn prior to randomization but after signing informed consent:

- Did not satisfy all inclusion/exclusion criteria
- Adverse event

- Lost to follow-up
- Withdrawal by subject (indicate reason)
- Physician decision
- Study terminated by Sponsor

For subjects discontinued or withdrawn after randomization but before completing the treatment period:

- Adverse event
- Death
- Lack of perceived efficacy by subject or investigator
- CrCl < 15 mL/min
- Lost to follow-up
- Protocol violation
- Study terminated by Sponsor
- Withdrawal by subject (indicate reason)
- Other (indicate reason)

A subject may be withdrawn due to non-compliance with any aspect of the protocol, as determined by the Investigator and/or the Sponsor's medical monitor or designee. Subjects who miss > 7 days of consecutive doses of study medication will be withdrawn from the study and early termination study procedures performed.

If the subject is withdrawn due to an adverse event, the Investigator will follow the subject until the adverse event has resolved or stabilized.

All subjects who are withdrawn from the study should complete protocol specified withdrawal procedures (Section 4.2.2).

4.2.2. Withdrawal Procedures

If a subject withdraws (or is withdrawn) from the study, the Investigator should complete and report all observations as thoroughly as possible up to the date of withdrawal, including the date of last treatment and the reason for withdrawal. Reasons recorded under "protocol violation" may include failure to comply with protocol requirements or study procedures, pregnancy, etc.

If the subject is withdrawn due to an AE, the Investigator should follow the subject until the AE has resolved or stabilized.

All subjects who are withdrawn from the study should complete all end-of-treatment/early termination procedures as soon as possible after early withdrawal. All subjects who are withdrawn from the study should return for post-treatment follow-up visits.

4.2.3. Subject Replacement

Subjects removed from the study for any reason will not be replaced.

4.2.4. Subject Re-screening Procedures

Re-screening of subjects is not permitted except with permission from the sponsor.

5. TREATMENTS ADMINISTERED

5.1. Investigational Products

The Investigator must ensure that the investigational product will be used only in accordance with the protocol.

The investigational products for this study are:

- DS-5565 7.5 mg tablets
- Placebo tablets matching DS-5565 7.5 mg tablets

5.1.1. Method of Assigning Subjects to Treatments and Blinding

Randomization will be performed centrally using an IXRS. At the Screening Visit, the Investigator, or other site personnel under the direction of the Investigator, should contact or access the IXRS to register the subject, obtain the SID, and record the subject's initials, date of birth, sex, and initial screening date. Upon confirmation of a subject's eligibility at the Randomization Visit, the Investigator, or designee, will contact the IXRS to register the subject as randomized and obtain the identification number of the initial study medication blister pack ("wallet") to be dispensed to this subject. At each on-treatment visit, the Investigator, or designee, should contact the IXRS to record the subject's visit and status and obtain the correct wallet number to be dispensed at that visit. Study medication should only be dispensed in accordance with IXRS instructions and wallet number assignment. At the End-of-treatment/Early Termination Visits, the subject's visit and status should also be recorded using the IXRS.

The randomization schedule will be generated by an independent statistician at the CRO and reviewed and approved by a statistician at Daiichi Sankyo who is independent of all other aspects of study conduct. The randomization schedule will be maintained by the independent statistician at the CRO and will be kept strictly confidential. IXRS and Clinical Supply Operations personnel will have access to medication identification codes but will remain blinded to treatment. All other personnel involved with the conduct and the interpretation of the study, including the Investigators, investigational site personnel, and Daiichi Sankyo employees, will be blinded to the treatment until after the database lock.

Randomization will be stratified by CKD strata through the IXRS. Eligible subjects will be randomized in the ratio of 2:1 to receive 13 weeks of treatment with DS-5565 7.5 mg QD or placebo for CrCl 15-29 mL/min or with DS-5565 7.5 mg BID or placebo for CrCl 30-59 mL/min. In order to maintain the blind, the package will have one of the following morning and night dose schemes (BID: 2 active; QD: 1 active + placebo; Placebo: 2 placebo).

5.1.1.1. Emergency Unblinding for Safety Reasons

In the case of a rare emergency where, in the investigator's opinion, unblinding of the treatment is necessary in order to evaluate further course of action, the investigator

should access the IXRS and follow the instructions to initiate subject unblinding. The investigator may also contact the sponsor or designee's Medical Monitor for information related to DS5565's adverse effects in making the decision to unblind. (Contact information – please refer to the Study Operations Manual, which contains the key Medical Monitoring study personnel and their contact information.)

The investigator should promptly document and report to the sponsor any unblinding (eg, accidental unblinding, unblinding due to a serious adverse event) of the investigational product(s).

In the event of unblinding, the subject will be informed about their treatment assignment (DS-5565 or placebo). If the subject is receiving DS-5565, the specific treatment group (7.5 mg QD or 7.5 mg BID) will not be revealed. Information about the treatment assignment must be restricted to designated study site staff/personnel that are providing immediate care to the subject. Any documentation of the treatment assignment must be maintained separately (i.e., a secured file). The information must not be included in the subject's source files to ensure the treatment assignment will remain blinded to the CRO monitor and other study personnel not involved with the subject's immediate care.

When an emergency unblinding has occurred, an automatic notification (via e-mail) will be sent to the Investigator and selected Daiichi Sankyo study personnel from the IXRS vendor. The notification will not contain any unblinding information. This will trigger the follow-up process to document the unblinding by completing the Emergency Unblinding by Investigator Form (to be provided by study personnel upon receipt of IXRS notification) and submit to Daiichi Sankyo Clinical Safety and Pharmacovigilance (CSPV); please refer to the form for completion instructions.

Once the study treatment has been unblinded, the study treatment should be discontinued, and the subject should leave the study treatment Phase. The subject will be seen for end-of-treatment assessments and follow-up, as defined in Section 6.5 and Section 6.6.

5.1.2. Method of Assessing Treatment Compliance

Records of treatment compliance for each subject will be kept during the study. The identification number of all dispensed and returned study drug wallets should be recorded, along with the SID. The number of tablets used and remaining in each wallet should be documented at each on-treatment visit and the End-of-treatment/Early Termination Visit. If any tablets have been removed from the wallets (but not taken), these should be counted, documented, and retained.

Treatment compliance will be calculated by dividing the number of doses taken by the number of doses assigned for the appropriate visit interval (adjusted for any changes in the visit interval). Compliance for each visit interval is defined as taking at least 80% of the study drug dosage prescribed for that interval. If a subject is noncompliant, the subject will be counseled by study staff on the importance of taking the correct amount of study medication. As the primary analysis will follow the intent-to-treat principle, subjects should not be discontinued from the study for treatment noncompliance unless the subject meets the discontinuation criteria outlined in Section 4.2.1.

5.1.3. Labeling and Packaging

Double-blind study medication will be provided in labeled blister cards (wallets). The blister label will include all information required by federal and local regulations. Additional details on the investigational drug products, such as the expiration date, can be found in documentation accompanying drug shipment.

Code-break envelopes or scratch-off labels will not be used for unblinding in this study. Unblinding of individual subjects will be controlled using the IXRS (see Section 5.1.1).

5.1.4. Preparation

Double-blind study drug will be provided to sites as fully prepared blister cards (wallets). All wallets will have 1 tablet for the morning dose and 1 tablet for the bedtime dose for each day of dosing for both QD and BID, as well as placebo.

Study treatment can be taken irrespective of food intake. Wallets will be individually numbered; only the correctly numbered wallet(s) should be distributed to study subjects in accordance with IXRS instructions.

5.1.5. Storage

Drug supplies must be stored appropriately in a locked cabinet in a room with limited and controlled access under the recommended storage conditions. The recommended storage conditions are provided with the shipment of drug supplies (on the carton and wallets of Investigational material).

NOTE: If storage conditions go outside of the recommended storage conditions, the site must not dispense the affected supplies (affected supplies should be placed in quarantine per IXRS requirements). Proper notification processes must be followed immediately after receipt of IMP identified as having a temperature excursion.

5.1.6. Drug Accountability

When a drug shipment is received, the Investigator or designee will check the amount and condition of the drug, check for appropriate local language in the label, drug expiration date (if available), and register receipt in IXRS. The Investigator or designee shall report a problem with the shipment via IXRS as soon as possible, as well as follow the instructions on the Template[®] instruction form as they pertain to any temperature excursions.

A Drug Accountability Record will be provided to each site for documenting the use of the investigational product. The record must be kept current and should include the date and quantity of drug (number of wallets) received at each shipment, the SID (and initials) of each randomized subject for whom the investigational product was dispensed, the wallet numbers, date and quantities of investigational product dispensed at each visit, amount of remaining or returned product received at each subject visit (including the number of tablets inside or outside of returned wallets), and the initials of the dispenser.

At the end of the study, or as directed, all study treatment, including unused, partially used, or empty wallets, and any drug that may have been removed from the wallets (but

not taken), will be destroyed locally. If a site or country does not have a means for destruction, the material will be returned to the shipping depot, as instructed by the Sponsor. Investigational product will be destroyed or returned only after the study monitor has completed a final inventory to verify the quantity to be returned. The return and/or destruction of IP are to also be processed through the IXRS.

At the end of the study, a final investigational product reconciliation statement must be completed by the Investigator, or designee, and provided to the Sponsor. Unused drug supplies may be destroyed by the Investigator when approved in writing by the Sponsor and the Sponsor has received copies of the site's drug handling and disposition standard operating procedures (SOPs). The return of Investigational Product must be documented and the documentation included in the shipment as well as contained within the packing slip.

All investigational product inventory forms must be made available for inspection by the Sponsor's authorized representative (eg, CRO site monitor) and any authorized inspector from a regulatory agency. The Investigator is responsible for the accountability of all used and unused study supplies at the site.

5.2. Concomitant Medications

5.2.1. Prohibited Medications

Use of concomitant medications that may confound assessments of safety or efficacy is not permitted during the study. This is particularly important for analgesics and/or other medications or therapies that may be intended specifically as treatments for FM.

Subjects who are receiving medication for FM (or any prohibited medication listed in [Table 5.1](#)) will be required to undergo drug washout prior to the Baseline Period. The Investigator should comply with product labeling instructions for drug discontinuation (eg, tapering of opioids to avoid side effects related to dependence). Minimum washout requirements for specific classes of prohibited medications are provided in [Table 5.1](#).

Subjects receiving treatment for FM should not begin washout of pain medication until they are determined to be potentially eligible for the study by the Investigator and contacted via telephone by the Investigator or designee.

Subjects should be instructed not to take any prohibited analgesic medicine, as listed on [Table 5.1](#), during the Baseline Period, prior to Randomization, or during the subsequent treatment period. Use of prohibited medications may necessitate subject discontinuation from the study.

Table 5.1: Prohibited Medications and Treatments - During Baseline and Treatment Periods

Medication Class/Example Drugs	Minimum Washout Period Prior to Collection of Pre-Randomization Baseline Pain Assessments ^a
Anticonvulsants, including pregabalin and gabapentin	3 days
Opioids, including tramadol; tapentadol	7 days
COX-1 and -2 inhibitors	3 days
Benzodiazepines	7 days
Tricyclic antidepressants and SNRI (eg, duloxetine)	7 days
Other: Non-benzodiazepine hypnotics, such as zolpidem, skeletal muscle relaxants, topical capsaicin, chromium picolinate, local anesthetics, α -lipoic acid, evening primrose oil, fatty acid supplements, and memantine	3 days

^a Investigators should also comply with product labeling recommendations for drug discontinuation. COX-1 and -2 = cyclooxygenase type 1 and 2

Non-pharmacological therapies for neuropathic pain, such as acupuncture, laser therapy, spinal cord stimulation, electrical nerve stimulation, surgery, initiation of psychological support, or any other treatment designed to modulate the perception of pain, are also prohibited during the study.

Subjects should be instructed to avoid excessive consumption of alcohol during the treatment period, as study drug may increase side effects of sleepiness and dizziness and potentiate the impairment of motor skills.

5.2.2. Allowable Medications

Use of SSRIs (but not SNRIs) is allowed if the subject has been on a stable dose for ≥ 90 days prior to screening and is not anticipated to need adjustment during the study period.

Aspirin (up to 160 mg/day) for myocardial infarction and stroke prophylaxis is permitted.

Acetaminophen/paracetamol (up to 2 grams/day in divided doses at intervals of 4-6 hours) is the sole rescue medication. The use of all pain-related medications including acetaminophen/paracetamol must be documented as a concomitant medication. The reason or indication for its use should also be recorded as an adverse event in the eCRF. The subject should be instructed on risks associated with acetaminophen/paracetamol overdose.

Any other non-study medication taken by the subject during the course of the study should be recorded as a concomitant medication on the eCRF. The condition or indication should be recorded as an adverse event, as appropriate, and the dose, route of administration, start and end-of-treatment, and other relevant information (eg, reason for use) should be documented.

Birth control medications are permitted.

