3.1.3. Study Endpoints

The primary safety endpoint is the safety and tolerability of renally adjusted doses of DS-5565 versus placebo.

Specific safety endpoints assessed include:

- All treatment-emergent adverse events (TEAEs)
- Change in clinical laboratory evaluations from baseline measured at randomization to Week 13/ET for DS-5565 versus placebo
- Change in neurological examinations from baseline to Week 13/ET for DS-5565 versus placebo
- Change in electrocardiograms from baseline to Week 13/ET for DS-5565 versus placebo
- Change in Columbia-Suicide Severity Rating Scale (C-SSRS) from baseline to Week 13/ET for DS-5565 versus placebo
- Assessment of Physician Withdrawal Checklist (PWC) at follow-up visits.

The secondary efficacy endpoints include:

- Changes in ADPS from baseline measured at randomization to Week 13/ET for DS-5565 versus placebo. Weekly ADPS is based on daily pain scores reported by the subject that best describes the worst pain over the previous 24 hours.
- Proportion of subjects with improvement in overall status at Week 13/ET as assessed by PGIC for DS-5565 versus placebo.

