4.1.1. Inclusion Criteria

Subjects must satisfy all of the following criteria to be included in the study:

1. Age \geq 18 years
2. Able to give written informed consent
3. Able to complete patient-reported questionnaires per the Investigator's judgment
4. Estimated CrCl between 15-59 mL/min from serum creatinine by the central laboratory using the Cockcroft-Gault equation
5. Fibromyalgia meeting American College of Rheumatology criteria for FM:
 - a. Widespread pain index (WPI) \geq 7 and symptom severity (SS) scale score \geq 5, or WPI 3 to 6 and SS scale score \geq 9,
 - b. Pain in at least 11 of 18 specific tender point sites,
 - c. Symptoms have been present at a similar level for at least 3 months, and
 - d. The subject does not have a disorder that would otherwise explain the pain

6. ADPS of ≥ 4 on the 11-point numeric rating scale (NRS) over the 7 days prior to randomization (based on completion of at least 4 daily pain assessments during the 7-day baseline period prior to randomization)
7. Women of child bearing potential (WOCBP) must be using adequate methods of contraception (as detailed in Section 4.1.3) to avoid pregnancy during the study and for 4 weeks after study completion.

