9. SAFETY ASSESSMENTS

9.1. Adverse Events

All clinical AEs occurring after the subject signs the ICF and up to 4 weeks after the last dose of study medication (i.e., follow-up period), whether observed by the Investigator or reported by the subject, will be recorded on the AE eCRF page. Medical conditions (including laboratory values/vital signs that are out of range) that were diagnosed or known to exist prior to informed consent will be recorded as part of medical history.

All clinical laboratory, vital sign, or ECG values should be appraised by the Investigator as to clinical significance. Isolated abnormal laboratory results, vital sign findings, or ECG findings should be reported as AEs if they are symptomatic, lead to study drug discontinuation, require corrective treatment, or are otherwise defined as an adverse event of special interest (AESI) [please refer to Section 9.7].

All SAEs are to be reported according to the procedures in Section 9.5. Always report the diagnosis as the AE or SAE term. When a diagnosis is unavailable, report the primary sign or symptom as the AE or SAE term with additional details included in the narrative until the diagnosis becomes available. If the signs and symptoms are distinct and do not suggest a common diagnosis, report them as individual entries of AE or SAE. For events that are serious due to hospitalization, the reason for hospitalization must be reported as the SAE (diagnosis or symptom requiring hospitalization). A procedure is not an AE or SAE, but the reason for the procedure may be an AE or SAE. Pre-planned (prior to signing the ICF) procedure or treatment requiring hospitalization for pre-existing conditions, which do not worsen in severity, should not be reported as SAEs (see Section 9.4.2 for Definitions). For deaths, the underlying or immediate cause of death should always be reported as an SAE. In addition, any serious, untoward event that may occur subsequent to the reporting period that the Investigator assesses as related to study drug should also be reported and managed as an SAE.

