11.6.1. Adverse Event Analyses

AEs will be coded using the Medical Dictionary for Regulatory Activities (MedDRA) classification system. A TEAE is defined as an AE that emerges during treatment (having been absent prior to treatment) or worsens relative to the pre-treatment state. The frequency of patients experiencing a specific TEAE will be tabulated by treatment, system organ class, preferred term, seriousness (see Section 9.4.2), worst severity (see Section 9.4.3), and relationship to study drug (see Section 9.4.4). Treatment-emergent AEs of special interest (defined in the SAP) will be summarized separately. In the by-subject analysis, a subject having the same event more than once will be counted only once. Listings of deaths, SAEs, and AEs leading to treatment discontinuation of a subject will be presented.

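### Does recording the reason for every rescue acetaminophen use as an adverse event put unchanged fibromyalgia pain into the TEAE tables?

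*Combined protocol and SAP*

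**What the plan says.** Section 5.2.2 (Allowable Medications) makes acetaminophen/paracetamol the sole rescue medication and has its use documented as a concomitant medication. It then adds: "The reason or indication for its use should also be recorded as an adverse event in the eCRF". The next paragraph covers any other non-study medication and is less absolute: "The condition or indication should be recorded as an adverse event, as appropriate".

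The entry criteria in section 4.1.1 ensure that the disease is present from the start. One reads: "Symptoms have been present at a similar level for at least 3 months". Another requires an ADPS of at least 4 "on the 11-point numeric rating scale (NRS) over the 7 days prior to randomization".

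Three other sections bear on how such a record is handled:

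- Section 9.1 says that medical conditions "diagnosed or known to exist prior to informed consent will be recorded as part of medical history".
- Section 9.4.1 leaves it to investigators to decide which circumstances count as adverse events.
- Section 11.6.1 gives the counting rule: "A TEAE is defined as an AE that emerges during treatment (having been absent prior to treatment) or worsens relative to the pre-treatment state". It then states the table: "The frequency of patients experiencing a specific TEAE will be tabulated by treatment, system organ class, preferred term, seriousness", followed by worst severity and relationship to study drug. A subject with the same event more than once is counted once.

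Section 3.1.3 lists all TEAEs first among the specific safety endpoints. Section 11.6 makes the safety analysis descriptive.

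**The concern.** The qualifier is missing for the one drug most likely to be taken for the disease under study. Section 3.1.5.1.1 itself notes that acetaminophen is in common use in this population, and section 5.2.1 prohibits other analgesics and fibromyalgia treatments. A site reading section 5.2.2 literally could therefore open an adverse event record the first time a subject takes rescue on treatment, even if the pain is what it was at baseline. The record would probably carry an onset date after the first dose.

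If such records were counted as TEAEs, the pain or fibromyalgia row and its system organ class row would partly measure rescue use, and so the disease, rather than harm from the drug. Rescue use could differ between arms, so the distortion need not cancel. Safety is the primary objective and the arms are small, so a few subjects would be visible in that row.

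**Working it through.** The point contests no figure in the plan, so the check is mainly a comparison of the sections. A short calculation then shows what a miscount would cost.

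**Step 1: what section 5.2.2 creates.** It creates an adverse event record. It does not say that the record is treatment-emergent, and it gives no rule for its onset date. An on-treatment onset is an inference about how sites would fill in the form.

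**Step 2: what the endpoint counts.** The endpoint and the table in section 11.6.1 count TEAEs, not all adverse event records. Section 9.1 collects events from consent until 4 weeks after the last dose, so the database will hold pre-treatment records in any case. Analysts must separate TEAEs from other records for every subject, and section 11.6.1 is the rule for doing so.

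**Step 3: apply the rule to the case in question.**

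| Reason for rescue on treatment | Absent before treatment? | Worse than before treatment? | TEAE under 11.6.1? |
|---|---|---|---|
| Fibromyalgia pain, unchanged | No | No | No |
| Fibromyalgia pain, worse | No | Yes | Yes |
| New complaint, such as a headache not present before | Yes | Not applicable | Yes |

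The second and third rows belong in the table. The first is excluded by the definition as written.

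**Step 4: what else limits the effect.** Section 9.1 already places known conditions in medical history. Medications are asked about at screening, during washout, at the Baseline Visit and at randomization (sections 6.1.1 to 6.3), so rescue use reported before the first dose is on record as pre-treatment. Section 9.4.4 classes an event reasonably explained by the disease under study as not related, so the related-TEAE count should normally be untouched. The rows for CNS events and oedema do not depend on this instruction, nor do the SAE, laboratory, ECG and C-SSRS results.

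**Step 5: size if the rule were ignored.** The inputs are about 60 subjects randomized (section 11.11) at 2:1 in each renal stratum (section 5.1.1).

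- Placebo: 60 × 1/3 = 20. One subject is 1/20 = 5.0 percentage points.
- DS-5565, both doses pooled: 60 × 2/3 = 40. One subject is 1/40 = 2.5 percentage points.

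Pooling the doses is an assumption. Section 5.1.1.1 treats 7.5 mg QD and 7.5 mg BID as separate treatment groups, section 11.6 summarizes by treatment group, and the split between strata is not given. If the doses are tabulated separately, the per-subject figure for each is larger than 2.5 points but cannot be fixed.

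The protocol gives no rescue rate, no share of subjects whose first use is on treatment, and no rate of misclassification. A total effect, or its direction, would have to be invented.

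**The case for a change.** The strongest case for acting is that the situation is foreseeable and no section addresses it by name. Section 5.2.2 does not refer to section 9.1 or section 11.6.1. Section 9.1 sends known conditions to medical history without saying that they cannot also be adverse events. Elsewhere the protocol does write such a rule: section 9.11.2 says how positive items on the withdrawal checklist are to be reported. Clearer wording would cost one sentence, while programmers often flag treatment emergence from dates.

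The inconsistency of wording stands, and so do the surplus records. The step to a wrong table does not, because it requires the analysts to replace the stated definition with a date rule that the protocol does not contain. The difference in wording may also be deliberate. Other non-study medications include long-term drugs for pre-existing conditions, where a qualifier is plainly needed. Acetaminophen is singled out in section 3.1.5.1.1 for its liver risk, although the protocol does not link that to the recording rule.

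There is a trade-off as well. Recording every reason and classifying afterwards keeps the judgement about worsening out of the moment of data entry. Asking sites to record only new or worse pain could lose real worsening, which in a safety study is arguably the worse error. Finally, section 11.2 defers detailed methods to a SAP to be prepared before unblinding, and section 9.5 refers to an eCRF Completion Guide. Neither was available, so it cannot be said that they are silent.

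**Conclusion.** No change to the plan is called for. The wording of section 5.2.2 is looser than that of its neighbours and may produce adverse event records for unchanged fibromyalgia pain. Under section 11.6.1 those records are not TEAEs, so the effect on the TEAE tables is zero when the plan is followed as written. A rule in the SAP to exclude them would repeat a definition that already excludes them. A cross-reference or a matching qualifier in section 5.2.2 would be tidy editing and would alter no result.

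This rests on one assumption: treatment emergence is judged against the pre-treatment state, as section 11.6.1 says, and not by onset date alone. If that failed, the consequence would be confined to one preferred-term row, its organ-class row and the overall TEAE counts, at the per-subject sizes shown above. No test or decision rule depends on them.
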